9.5 Follow-up Assessments

Patients will be followed for 6 months after cessation of study treatment for survival.

Patients removed from therapy without evidence of progression will undergo radiological examination every 12 weeks or earlier, if clinically warranted.

Patients will be followed for SAEs for 90 days after the cessation of treatment

10 CRITERIA FOR EVALUATION AND ENDPOINT

10.1 Efficacy

The primary objective is ORR with a secondary objective of PFS6. Evaluable subjects will be all patients who complete at least one set of disease assessment scans after starting protocol treatment. Patients who discontinue therapy due to clinical progression will also be considered evaluable even if they do not have a set of disease assessment scans.

Patients who discontinue treatment prior to one disease assessment evaluation will be deemed unevaluable and need to be replaced except if the patient was determined to have clinical progression as the reason for discontinuation of therapy. Disease assessments will be measured by CT or MRI scan. All evaluations and treatment decisions will be based on RECIST v1.1 criteria.^{28, 29} The iRECIST criteria³⁰ will be used as an exploratory measurement of efficacy which may be performed retrospectively.

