9. Coagulation labs to be collected: PT/INR, APTT. Coagulation panel will only be required at EOT if patients are on active anticoagulant therapy and require monitoring.
10. Free T4, Free T3 and TSH must be performed at baseline and at least every 4th cycle during treatment
11. Pregnancy test (serum or urine- if urine is positive it must be confirmed with serum test) must be done at screening for all women of childbearing potential and every even cycle (2,4,6 ...etc.) during treatment (must be completed within 72hr prior to study enrollment)
12. ECG should be collected at screening (see section 9 for QTcF eligibility details at screening) and at every 4th cycle.
13. CT scans of chest, abdomen and pelvis will be repeated every 4th cycle during treatment within 1 week prior to the corresponding cycle (e.g., prior to cycle 5, 9, 13... etc.). However, if the study treatment is delayed, scans can be delayed to correspond to the treatment schedule, and this will not be a deviation. CT scans will be done at the end of treatment visit only if patient has come off for reasons other than progression. Use of contrast according to institutional practice is recommended but not required.
14. Bone Scans if clinically indicated for evaluation of bone metastatic disease
15. For participants who opt in to the optional tissue collection, tissue may be collected at pre-screening from an urothelial carcinoma diagnostic procedure (soft tissue biopsy or TURBT) or during screening from a soft tissue biopsy (only for patients who do not sign the pre-screening ICF). Subjects are also offered the option of a fresh soft-tissue biopsy or TURBT again prior to treatment at cycle 4 or after. See Section 14 for details.
16. For participants who opt in to the optional blood collection, blood may be collected on C1D1, C2D1, C4D1, C7D1, C13D1, and at end of treatment. See Section 14 for details.
17. For participants who opt in to the optional stool collection, stool may be collected and stool questionnaire administered within 3 days prior to treatment on C1D1, C2D1, C4D1, C7D1, C13D1, and at end of treatment. See Section 14 for details.
18. Cabozantinib at dose specified in dose escalation and specified in section 6.2. Subjects will complete dosing diary for each cycle (Appendix I)
19. Pembrolizumab 200 mg IV q3weeks
20. End of treatment visit should occur within 28 (± 14) days after subject completes study treatment

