- PT/INR, aPTT if patients are on active anticoagulant therapy and require monitoring
- B-type Natriuretic peptide
- Urinalysis including urine protein creatinine ratio

Optional Blood and Stool Collection and administration of Stool Questionnaire for correlatives see section 14

Adverse event collection for 30 days

CT scans of the chest/abdomen/pelvis and response assessment by RECIST v1.1 to be performed at the end of treatment visit only if patient has come off for reasons other than progression

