10.1.1 RECIST v1.1

Responses for Phase II patients must be confirmed as follows:

- Partial or complete responses (PR or CR, respectively) must be confirmed by repeat imaging performed 4 to 6 weeks after the first assessment showing PR/CR.
- Stable disease (SD), measurements must have met the SD criteria at least once after study entry at a minimum interval of 9 weeks.
- Patients with progressive disease (PD) who are receiving clinical benefit in the opinion of the investigator will be allowed to continue on treatment after the first evidence of PD. Repeat imaging to confirm PD should be performed according to the schedule of events (9 weeks after the scan showing first evidence of progression) or sooner at the discretion of the investigator but at least 4 weeks after the first evidence of progression.
- Patients who are experiencing unequivocal RECIST v1.1 disease progression or who are not receiving clinical benefit in the opinion of the investigator will not require repeat imaging.

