11 STATISTICAL CONSIDERATIONS

11.1 Primary objective

This is a non-randomized phase II trial designed to evaluate the combination of pembrolizumab plus cabozantinib. Prior clinical trials of first-line gemcitabine-carboplatin in cisplatin-ineligible patients have been performed. One study identified an objective response rate of 36%, with a median progression-free survival of only 4.8 months in 56 treated patients.²³ A second study of 60 patients noted an objective response rate of 38.4%, with a median progression-free survival of 7.6 months.²⁴ It has also been reported a 26% ORR in patient treated with pembrolizumab with locally advanced or metastatic urothelial cancer²⁵. ORR will be analyzed descriptively. The proportion of objective responses will be reported and a 95% one-sided exact binomial confidence interval (Clopper-Pearson) will be calculated for ORR. With 35 evaluable subjects the lower bound of the 95% confidence interval will extend no more than 26% from the observed proportion. If there are 17 or more objective responses in 35 patients the confidence interval will exclude 32%. Adding another 10% for unevaluable patients that may be enrolled, a total of up to 39 patients will be enrolled.

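### The primary ORR drops and replaces treated patients who stop before any scan, no all-treated ORR is planned, and section 10.1 contradicts itself on patients first scanned at end of treatment

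*Combined protocol and SAP*

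**What the plan says.** Section 10.1 defines the response population: "Evaluable subjects will be all patients who complete at least one set of disease assessment scans after starting protocol treatment". Patients who stop for clinical progression without a scan are added to it. A later sentence in the same section says: "Patients who discontinue treatment prior to one disease assessment evaluation will be deemed unevaluable and need to be replaced", again excepting clinical progression.

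Section 11.1 builds the primary result on this population. It calls the ORR analysis descriptive, specifies a one-sided 95% Clopper-Pearson interval, and states the benchmark: "If there are 17 or more objective responses in 35 patients the confidence interval will exclude 32" per cent. On enrolment it says: "Adding another 10% for unevaluable patients that may be enrolled, a total of up to 39 patients will be enrolled".

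Three other places bear on who gets a scan:

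- Study Calendar, note 13: "CT scans will be done at the end of treatment visit only if patient has come off for reasons other than progression". Section 9.4 says the same and adds a RECIST assessment. The visit falls 28 ± 14 days after treatment ends.
- Section 9.5: "Patients removed from therapy without evidence of progression will undergo radiological examination every 12 weeks or earlier, if clinically warranted".
- Section 10.1.1: a partial or complete response "must be confirmed by repeat imaging performed 4 to 6 weeks after the first assessment showing PR/CR".

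No section plans an ORR over all treated patients. Section 11.2 mentions a proportion of subjects with a response but gives no denominator. The one-dose population in section 10.2 is for safety only.

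**The concern.** A patient who starts treatment and stops before any scan has not responded. If the reason is toxicity, withdrawal, intercurrent illness or a death not recorded as progression, section 10.1 takes that patient out of the denominator and enrols another. As an estimate for treated patients, the ORR can then only stay the same or go up. The exposure period is long: cycles last 3 weeks and the first on-treatment CT is due in the week before cycle 5, at about weeks 11 to 12.

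Because the analysis is descriptive, the evaluable-set ORR and its lower bound are the headline result, and no all-treated figure stands beside them. The safety tables would cover every dosed patient, while the ORR could omit some who stopped because of toxicity.

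The second problem is that the denominator is not fixed. A patient who stops early for a reason other than progression is due a CT at the end-of-treatment visit. If that is the first post-baseline scan, the two sentences of section 10.1 classify the patient in opposite ways. In an open-label single-arm trial, that choice could be made after the outcome is known.

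**Working it through.** **Inputs.** From 11.1: 35 evaluable, one-sided 95% Clopper-Pearson, benchmark 17 of 35 against 32%, 10% allowance, cap of 39. Assumption: dropped patients have no post-baseline scan and count as non-responders. The documents do not say how many early stoppers will have the end-of-treatment CT.

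**Step 1: reproduce the plan's figures.** The lower bound for x responses in n is the 5% quantile of Beta(x, n − x + 1).

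- 16/35: 31.2%
- 17/35: 33.8%

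So 17 is the smallest count that excludes 32%, as stated. P(X ≥ 17 | n = 35, p = 0.32) = 0.0302. For enrolment, 35/0.90 = 38.9, which rounds up to 39.

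**Step 2: restore the dropped patients.** The table gives one-sided 95% lower bounds by number treated.

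| Treated | Dropped | ORR with 17 | Bound with 17 | Excludes 32%? | Bound with 18 | Smallest count excluding 32% (tail probability at 32%) |
|---|---|---|---|---|---|---|
| 35 | 0 | 48.6% | 33.8% | yes | 36.5% | 17 (0.0302) |
| 36 | 1 | 47.2% | 32.8% | yes | 35.3% | 17 (0.0405) |
| 37 | 2 | 45.9% | 31.8% | no | 34.3% | 18 (0.0256) |
| 38 | 3 | 44.7% | 30.9% | no | 33.3% | 18 (0.0344) |
| 39 | 4 | 43.6% | 30.0% | no | 32.3% | 18 (0.0453) |

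One dropped patient does not change the reading. Two or more do, and the plan has room for 39 − 35 = 4.

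**Step 3: chance of meeting the benchmark.** Let the true all-treated ORR be 32%, and let a fraction q of treated patients, all non-responders, be dropped. The evaluable-set ORR is then 0.32/(1 − q), and the chance of meeting the benchmark is P(X ≥ 17 | 35, 0.32/(1 − q)).

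| q | Evaluable ORR | Chance of 17 or more of 35 |
|---|---|---|
| 0 | 32.0% | 3.0% |
| 5% | 33.7% | 4.9% |
| 10% | 35.6% | 7.8% |
| 15% | 37.6% | 12.4% |

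The chance passes 5% at q of about 5.3%. The 10% row uses the plan's own allowance and assumes that all of it is treated patients who are never scanned, which is an upper case; 5% and 15% are assumptions for range. These figures are conditional on reaching 35 evaluable patients, which at q = 10% has probability P(at least 35 of 39) = 0.65.

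**Step 4: the conflict.** Take a patient who stops for toxicity in cycle 2, before any on-treatment CT, and has the scheduled end-of-treatment CT about four weeks later. The definition in 10.1 asks only for a set of scans after starting treatment, so the patient is evaluable. The replacement sentence looks at whether treatment stopped before an assessment, which it did, so the patient is unevaluable and replaced. No section says which sentence governs.

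**The case against.** The strongest reply is that no test is inflated. Section 11.1 states no null hypothesis, alpha, power or decision rule, and 17 of 35 only illustrates precision. That is right: 7.8% is the chance of meeting a benchmark, not a type I error of this trial, and the interval remains valid for the evaluable set. But the estimate and its bound are the whole primary result, so the population they describe still matters.

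The evaluable set is also disclosed in advance and keeps patients who stop for clinical progression. This protects one reason for stopping and depends on that reason being recorded.

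The end-of-treatment CT may bring many early stoppers back, so that few are lost; at 2.5% dropped the chance is only 3.8%. That holds only if the definition governs over the replacement sentence. If the replacement sentence governs, some removed patients do have scans and could in principle have a response, so the upward-only argument covers only patients with no post-baseline scan.

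The 10% allowance may include enrolled patients who were never dosed, whom an all-treated denominator also leaves out. This is why 10% is labelled an upper case.

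Section 11.2's undefined proportion of subjects could be read as everyone, but without a denominator it does not plan an all-treated ORR. The two sentences of 10.1 can be harmonised by reading the second as no assessment ever obtained. That is a sensible reading, but the text does not say it.

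**Conclusion.** The concern holds and should be fixed. As written, the plan removes treated patients without a scan from the primary ORR unless clinical progression was the reason for stopping, plans no all-treated figure, and leaves open how to classify patients first scanned at end of treatment. For never-scanned patients the bias can only be upward. With 17 responses, one dropped patient leaves the exclusion of 32% intact, and two to four lose it. The rise from 3.0% to 7.8% in the chance of meeting the benchmark rests on a true all-treated ORR of 32% and on the full 10% allowance being treated, never-scanned non-responders. The actual size depends on how many early stoppers have the end-of-treatment CT, which the documents do not give. The textual findings are firm; the size is a range.

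**What to change.** Change the wording of sections 10.1 and 11.1 as follows:

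- Make the primary ORR denominator all patients who receive at least one dose of study treatment. Count those with no post-baseline assessment as non-responders.
- Reconcile the two sentences of 10.1 so that any post-baseline scan, including the end-of-treatment CT, counts as a disease assessment.
- State the descriptive benchmark by number treated: 17 responses for 35 or 36 treated, 18 for 37 to 39. This covers every count from 35 to the cap, so replacement towards 35 evaluable patients can continue without affecting it.
- Report the evaluable-set ORR as a sensitivity analysis.

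No extra patients or scans are needed, because the end-of-treatment CT is already scheduled. The cost is an amendment with the approvals in section 15.8, a slightly lower reported ORR, and one more response needed for the benchmark if 37 to 39 patients are treated.

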10.1.1 RECIST v1.1

Responses for Phase II patients must be confirmed as follows:

- Partial or complete responses (PR or CR, respectively) must be confirmed by repeat imaging performed 4 to 6 weeks after the first assessment showing PR/CR.
- Stable disease (SD), measurements must have met the SD criteria at least once after study entry at a minimum interval of 9 weeks.
- Patients with progressive disease (PD) who are receiving clinical benefit in the opinion of the investigator will be allowed to continue on treatment after the first evidence of PD. Repeat imaging to confirm PD should be performed according to the schedule of events (9 weeks after the scan showing first evidence of progression) or sooner at the discretion of the investigator but at least 4 weeks after the first evidence of progression.
- Patients who are experiencing unequivocal RECIST v1.1 disease progression or who are not receiving clinical benefit in the opinion of the investigator will not require repeat imaging.

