6 TREATMENT PLAN

Treatment should be administered on Day 1 of each cycle after all procedures and assessments have been completed as detailed on the Study Calendar (Section 8). Trial treatment may be administered up to 3 days before or after the scheduled Day 1 of each cycle.

All trial treatments will be administered on an outpatient basis.

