8 STUDY CALENDAR

1 cycle = 3 weeks ± 3 days

Examination	Pre-screening ²³	Screening ¹	C1, 5, 9... Day 1 ²	C2, 6, 10... Day 1	C3, 7, 11... Day 1	C4, 8, 12... Day 1	End of Treatment ²⁰	Follow-up ²¹
Informed consent	X	X						
Medical history		X						
Eligibility criteria	X	X						
Vital signs, weight		X	X	X	X	X	X	
Height		X						
Physical examination ³	X	X	X	X	X	X	X	
ECOG performance status		X	X	X	X	X	X	
Viral Hepatitis Screening ⁴	X							
Smoking History		X						
Hematology ⁵	X	X	X	X	X	X	X	
Chemistry ⁶	X	X	X	X	X	X	X	
LDH, Lipase, Lipid Panel, GGT ⁷	X					X	X	
BNP ²²		X				X	X	
Urinalysis ⁸	X	X	X	X	X	X	X	
Coagulation ⁹	X					X	X	
Thyroid Function Test ¹⁰	X					X	X	
Pregnancy test ¹¹	X		X			X		
ECG ¹²		X				X		
Concomitant Medications					X			
Adverse Event Assessment					X			
CT Scans (c, a, p) ¹³	X					X ¹³	X	X ²¹
Bone Scans ¹⁴	X	X					X	X
Optional Tissue for Correlative Studies ¹⁵	X	(X) ¹⁵				X		
Optional Blood for Correlative Studies ¹⁶			X	X	X	X	X	
Optional Stool for Correlative Studies ¹⁷			X	X	X	X	X	
Optional Stool Questionnaire to accompany Optional Stool sample collection for Correlative Studies ¹⁷			X	X	X	X	X	
Cabozantinib ¹⁸			X	X	X	X		
Pembrolizumab ¹⁹			X	X	X	X		
Survival Follow Up								X ²¹

1. Screening procedures must be completed within 28 days prior to C1D1 ALL Pre-study/Screening procedures should be completed within 4 weeks of study enrollment - with the exception of laboratory tests which need to be completed within 14 days prior to study treatment.
2. Labs on C1D1 do not need to be repeated if conducted within 14 days of start of treatment
3. Physical Exam including oral examination
4. Hepatitis screening will be performed at screening if clinically indicated.
5. Hematology includes CBC with differential and platelets (must be completed within 2 weeks prior to study enrollment).
6. Chemistry includes Albumin, Alkaline Phosphatase, Aspartate Aminotransferase, Alanine Aminotransferase, Total Bilirubin, Calcium, Carbon Dioxide, Creatinine, Chloride, Glucose, Potassium, Protein, Sodium, Urea Nitrogen, phosphorus and magnesium (must be completed within 14 days prior to study enrollment at screening)
7. Additional Labs: Lactate Dehydrogenase, Lipase, Lipid Panel, Gamma Glutamyl Transferase, and should be collected at baseline and at every 4th cycle.
8. Urinalysis including urine protein/creatinine ratio on day 1 of each cycle. Both spot protein/creatinine and the 24 protein/creatinine evaluations are acceptable.

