9.3 On-Treatment Evaluations

Physical Exam – **at each cycle**

ECOG Performance Status – at each cycle

Vital Signs (Incl. weight) – at each cycle

Labs: (do not need to be repeated if screening labs performed within 14 days of C1D1)

- CBC w/diff – **at each cycle**
- CMP – Albumin, Alkaline Phosphatase, Aspartate Aminotransferase, Alanine Aminotransferase, Total Bilirubin, Calcium, Carbon Dioxide, Creatinine, Chloride, Glucose, Potassium, Protein, Sodium, Urea Nitrogen, phosphorous and magnesium. – **at each cycle**
- Additional Labs: LDH, Lipase, Lipid Panel, Gamma Glutamyl Transferase, N-type Natriuretic peptide – **at every fourth cycle (4, 8, 12...)**
- Coagulation – PT/INR, APTT – at every fourth cycle (4, 8, 12...)
- Thyroid function – TSH, Free T4, Free T3 – at every fourth cycle (4, 8, 12...)
- Serum pregnancy test (for women of childbearing potential) at every even cycle **(2, 4, 6...)**
- Urinalysis including urine protein creatinine ratio – **at every cycle**

ECG – at every fourth cycle (4, 8, 12...)

Safety assessment - Monitoring and recording all adverse events and serious adverse events using the CTCAE version 5.0 – **at each cycle**

Review of concomitant medications – **at each cycle**

CT scans of the chest/abdomen/pelvis and response assessment by RECIST v1.1 to be **repeated every 4th cycle**. However, if the study treatment is delayed, scans can be delayed to correspond to the treatment schedule, and this will not be a deviation.

Bone Scans if clinically indicated

Optional Tissue Collection for correlates at **cycle 4**, or after, see section 14

Optional Blood and Stool Collection and administration of Stool Questionnaire for correlates – **at C1D1, C2D1, C4D1, C7D1, C13D1** see section 14

Treatment with 200mg pembrolizumab per section 6.3

Treatment with appropriate dose of cabozantinib – review of patient dosing diary per section 6.2

9.4 End of Treatment Assessments (completed 28 days ± 14 days after completion of treatment)

Physical exam

Vital Signs

Concomitant medication collection

ECOG Performance status

Labs:

- CBC w/diff
- CMP – Albumin, Alkaline Phosphatase, Aspartate Aminotransferase, Alanine Aminotransferase, Total Bilirubin, Calcium, Carbon Dioxide, Creatinine, Chloride, Glucose, Potassium, Protein, Sodium, Urea Nitrogen. Phosphorus and magnesium
- Additional Labs: LDH, Lipase, Lipid Panel, Gamma Glutamyl Transferase, B-type Natriuretic peptide
- Thyroid function – TSH, Free T4, Free T3

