10.1.2 Evaluation of Best Overall Response

The best overall response is the best response observed until progression/recurrence and is determined as indicated in the table below:

Target Lesions	Non-Target Lesions	Evaluation of New Lesions	Best Overall Response
CR	CR	No	CR
CR	SD	No	PR
PR	Non-PD	No	PR
SD	Non-PD	No	SD
PD	Any	Yes or No	PD
Any	PD	Yes or No	PD
Any	Any	Yes	PD

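### Response confirmation is required at 4 to 6 weeks, but the listed CTs are about 12 weeks apart and the best-response rule has no confirmation step, so a durable response can count under one rule and fail the other

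*Combined protocol and SAP*

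**What the plan says.** Section 10.1.1 opens with "Responses for Phase II patients must be confirmed as follows" and requires that a PR or CR "must be confirmed by repeat imaging performed 4 to 6 weeks after the first assessment showing PR/CR". The next subsection, 10.1.2, defines the outcome differently: "The best overall response is the best response observed until progression/recurrence". Its table maps lesion categories to a best response and has no confirmation step.

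The imaging schedule is in two other places. Section 8, footnote 13: "CT scans of chest, abdomen and pelvis will be repeated every 4th cycle during treatment within 1 week prior to the corresponding cycle", with cycles 5, 9 and 13 as examples. Section 9.3 has CT and response assessment "repeated every 4th cycle". Both allow scans to slip later when treatment is delayed. Neither mentions a confirmatory scan.

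The timing windows are "Trial treatment may be administered up to 3 days before or after the scheduled Day 1 of each cycle" (Section 6) and "1 cycle = 3 weeks ± 3 days" (Section 8). An end-of-treatment CT is done unless the patient stopped for progression; footnote 20 of Section 8 says "End of treatment visit should occur within 28 (± 14) days after subject completes study treatment". Patients who stop without progression are then imaged every 12 (±1) weeks, or sooner on clinical grounds (Section 8, footnote 21).

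The synopsis and Sections 1.1 and 11.1 name ORR as the primary endpoint without saying whether responses must be confirmed. Section 11.1 treats ORR descriptively, with a one-sided 95% Clopper-Pearson interval, and notes that 17 responses in 35 evaluable patients would exclude 32%.

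**The concern.** ORR is the only primary endpoint, so its numerator should follow from one rule. Here two adjacent subsections give different answers for the same patient. Take a PR first seen before cycle 5 (week 12) and still present before cycle 9 (week 24), with no scan between. It is durable and was imaged on the listed schedule. It fails the 4 to 6 week requirement, yet it is the best response observed.

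Sites working from the calendar and Section 9.3 are not directed to the extra scan, so this case is foreseeable. In an open-label, single-arm trial, the choice between the two rules should not be left until responses are known.

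**Working it through.** **1. The plan's own figure.** The one-sided 95% Clopper-Pearson lower bound for x responses in n = 35 is the 0.05 quantile of Beta(x, 35 − x + 1).
- x = 17 (48.6%): lower bound 33.8%, which excludes 32%.
- x = 16 (45.7%): lower bound 31.2%, which does not.

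The statement in Section 11.1 reproduces. The matching exact tail probabilities at a true rate of 32% are 0.030 for 17 or more and 0.062 for 16 or more.

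**2. Required interval (Section 10.1.1).** 4 to 6 weeks = 28 to 42 days.

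**3. Gap between consecutive listed on-treatment CTs (Sections 6, 8 and 9.3).**
- Nominal: 4 × 21 = 84 days.
- Minimum if the ±3 days applies to each scheduled Day 1: the latest cycle 5 CT is on Day 1 given late, 84 + 3 = day 87. The earliest cycle 9 CT is 7 days before a Day 1 given early, 168 − 3 − 7 = day 158. Gap 158 − 87 = 71 days, which is 71 − 42 = 29 days past the window.
- Minimum if each cycle may be 3 days short and this accumulates: 4 × (21 − 3) − 7 = 65 days, which is 65 − 42 = 23 days past the window.

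On either reading, two consecutive listed on-treatment CTs cannot satisfy 10.1.1. Treatment delays only lengthen the gap.

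**4. Could another listed scan fall in the window?**
- End-of-treatment CT, 28 ± 14 = 14 to 42 days after treatment ends. If treatment ends L days after the response scan, the earliest CT is at L + 14. L + 14 ≤ 42 requires L ≤ 28. It can therefore confirm only for patients who stop within 28 days of the response scan.
- Follow-up scan, 12 ± 1 weeks = 77 to 91 days. Counted from the last scan, it is always outside the window. Counted from the end of treatment, and for a response first seen on the end-of-treatment CT, the gap runs from 77 − 42 = 35 to 91 − 14 = 77 days. A gap of 42 days or less requires that CT on day 77 − 42 = 35 or later, so on days 35 to 42.

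Neither route covers a responder who stays on treatment.

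**5. The week 12 and week 24 responder with no scan between.**

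| Rule | Result |
|---|---|
| 10.1.1, read literally | Not confirmed in the window: not a response |
| 10.1.2 | PR or CR is the best response observed: counts |
| Synopsis, 1.1, 11.1 | Do not say which applies |

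The patient is in the denominator either way, because Section 10.1 makes a patient evaluable after one set of post-baseline scans.

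**The case against.** The strongest reply is that there is no clash. Section 10.1.1 itself orders the scan; it is triggered by an event, and a fixed calendar cannot date it. Nothing says the listed CTs are the only ones allowed. Read literally, 10.1.1 also settles the count, because a response not confirmed in the window is not a confirmed response. Subsection 10.1.2 sits beside it and does not waive the requirement.

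Much of this stands. A reader might infer that responses cannot be confirmed under this protocol, or that nothing in it says how a response re-imaged outside the window counts. The documents support neither: the extra scan is ordered, and the literal reading gives an answer. Confirmed ORR is the more natural reading.

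What remains is that this answer discards a durable response shown on the protocol's own scans, that 10.1.2 gives the opposite answer, and that the primary-endpoint text does not choose. Section 10.1 refers all evaluations to RECIST v1.1, but the protocol sets its own bounded window, and a general reference does not say what happens outside it.

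It is also fair that ORR is descriptive, with no formal success rule, and that one patient matters at any binomial cut-off. That limits the size of the point but does not remove it.

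**Conclusion.** The point holds as a mismatch between the confirmation rule, the imaging schedule and the best-response rule, and it should be fixed before the primary analysis. No two consecutive listed on-treatment CTs can confirm a response: they miss the window by at least 23 to 29 days, depending on how the visit windows are read. A durable response without a correctly timed extra scan is therefore classified in opposite ways by 10.1.1 and 10.1.2.

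The effect on ORR cannot be sized. The documents do not give the share of responses that would be re-imaged outside the window, and it is zero if every ordered scan is done on time. A reader might infer that the reported ORR will be biased by a material amount; nothing in the documents shows that. What can be shown is the sensitivity at the benchmark in Section 11.1, where one reclassified patient moves the lower bound from 33.8% to 31.2%, across 32%. This assumes 35 evaluable patients.

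A separate, minor point does not touch the ORR numerator. For confirming progression, 10.1.1 attributes a 9-week interval to the schedule of events, the calendar interval is 12 weeks, and Section 6.9 gives 4 to 8 weeks. These passages must be reconciled.

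**What to change.** Before the primary analysis:
- Define ORR in the synopsis and Sections 1.1, 10.1.2 and 11.1 as confirmed CR plus PR.
- Cross-reference the 4 to 6 week confirmatory scan in Sections 8 and 9.3.
- In 10.1.1, accept as confirmation any repeat scan at least 4 weeks after first PR/CR that still shows response: the 4 to 6 week scan where done, otherwise the next scheduled, end-of-treatment or follow-up scan.
- Count evaluable patients without such a scan as non-responders.
- Report two sensitivity analyses with the same Clopper-Pearson bound: ORR under the strict 4 to 6 week rule, and best-observed (unconfirmed) ORR.
- Record the date of the change and what response data were known then.
- Separately, reconcile the progression-confirmation intervals in 10.1.1, the calendar and 6.9.

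Cost: no scan beyond those the protocol already orders or lists. It does need an amendment with the approvals in Section 15.8 (the drug manufacturer and the IRB, plus FDA review if scientific quality is significantly affected). The primary rule also becomes wider: the confirmed count can only equal or exceed the strict 4 to 6 week count, and can only equal or fall below the unconfirmed count. The two sensitivity analyses show both differences.
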